4.2 Outline of Schedule

4.2.1 Screening and Baseline Evaluations:

4.2.1.1 Screening Evaluations

The following screening assessments must be done to determine eligibility for study participation. Written consent from parents(s)/guardian(s) will be obtained before conducting any study procedures.

- Screen for age and weight entry criteria (see Section 5).
- Medical history.
- Physical examination including body weight.
- Severe pneumonia (based on WHO criteria).
- Peripheral blood oxygen saturation (SpO₂) by pulse oximetry on air.
- Capillary blood gas with lactate (P_aO₂, P_aCO₂, pH, base excess, lactate) to evaluate for acidosis and hypercapnia.
- Completion of SICK score form (based on physical exam and SpO₂) data.
- Rapid hemoglobin and complete blood count (CBC).

- Malaria rapid diagnostic test.
- Point of care blood glucose.
- Comprehensive metabolic panel will be obtained *only* if indicated as part of standard care.

4.2.1.2 Baseline (Pre-treatment) Evaluations

Once eligibility criteria are met, baseline assessments are obtained. Any baseline assessment obtained during the Screening period will be used as the baseline value.

- Vitals signs and capillary refill time.
- Record concomitant medication information.
- Determine mask size to be used in line with body weight. Patients with a body weight of 8-13 kg will receive treatment with a small 30 ml mask and patient with a body weight of 14-26 kg will receive treatment with a large 50 ml mask.
- Peripheral blood oxygen saturation (SpO₂) by pulse oximetry on oxygen.

4.2.2 Investigational Treatment Periods

4.2.2.1 Period 1

Patients will be placed on supplemental oxygen consistent with standard of care.

(Group A): Nasal Reservoir plus Nasal Cannula (1 hr duration) (Group B): Nasal Cannula (1 hr duration)

- Continuous monitoring of peripheral blood oxygen saturation (by pulse oximetry) with recordings every 15 min.
- Continuous end-tidal carbon dioxide (CO₂) monitoring with recordings every 15 min.
- Record vital signs every 15 min.
- Record oxygen flow (L/min) every 15 min.
- Record concomitant medication information.
- Record adverse event information.
- Physical examination, including capillary refill time; capillary blood gases (PaO₂, PaCO₂, pH, base excess, lactate); and completion of SICK score form at end of Period 1.

4.2.2.2 Period 2

(Group A): Nasal Cannula Alone (1 hr duration)

(Group B): Nasal Reservoir and Cannula Alone (1 hr duration)

- Continuous monitoring of peripheral blood oxygen saturation (by pulse oximetry) with recordings every 15 min.
- Continuous end-tidal carbon dioxide (CO₂) monitoring with recordings every 15 min.
- Record vital signs every 15 min.
- Record oxygen flow (L/min) every 15 min.
- Physical examination, including capillary refill time; capillary blood gases (PaO₂, PaCO₂, pH, base excess, lactate); and completion of SICK score form *at end of Period* 2.

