Methods of oxygen conservation (termed "oxygen conserving devices") have included both changing the interface (e.g., reservoir cannulas and transtracheal catheters) and changing the oxygen delivery system. Reservoir cannulas, a more common oxygen-conserving device, function by storing oxygen in the reservoir space during exhalation, making that oxygen available as a bolus upon the onset of the next inhalation (Soffer et al., 1985; Tiep and Carter, 2016). Oxygen is conserved because the patient breathes a higher concentration of oxygen without increasing flow from the oxygen tank or concentrator. Reservoir cannulas increase the percent of oxygen in the air that the patient inhales over that delivered by standard nasal cannula and usually enable a reduction in the oxygen flow setting of approximately 25 to 50 percent while maintaining the same pulse oxygen saturation. The development of oxygen conserving devices was based on efforts to improve the portability of oxygen therapy by reducing the liter flow and thereby enabling patients to use a smaller and lighter ambulatory system, or a standard system for longer time periods (Hofmann 1994). Other advantages include a reduction of overall costs of long-term oxygen therapy and the ability to treat refractory hypoxemia more effectively.

Tables 1 and 2 show typical gas, liquid, and concentrator oxygen systems – and oxygen-conserving devices (American Thoracic Society 2015), many of which are not readily available or practical in resource-limited settings.

Table 1. Gas, Liquid and Concentrator Oxygen Systems

Features	Concentrator	Cylinder (Compressed Gas)	Liquid

Reliability	Good with regular maintenance	Good but gauges may become inaccurate	Generally good but connector may freeze
Cost	Least expensive but cost of electricity born by patient	Higher	Highest
Powerwall current	Required	Not required	Not required
Transfilling	Good only on special units that allow transfilling	Limited	Excellent
Ambulatory use	Good with transfill systems to gas plus conserver	Good with conserver	Good alone and with conserver
Stationary weight	35-50 lb	H cylinder 200 lb	Reservoir 120 lb
Use time at 2 L⋅min ⁻¹	Continuous	2.5 days	8.9 days, special system >30 days
Portable weight	Portable units are not presently available	E cylinder 22 lb with cart	6 lb with no conserver
Use time at 2 L⋅min ⁻¹	Unlimited	5 h	4 h
Portable weight with conserver	See gas transfill portable with conserver	M6 cylinder 4.5 lb	3.4 lb with conserver

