2.3 Global Good/Intellectual Ventures Pediatric Mask (Nasal Reservoir Cannula)

Improving oxygen delivery and extending oxygen supplies to ill patients with respiratory distress can reduce fatalities in resource-poor settings. Global Good has developed a low cost oxygen mask (nasal reservoir cannula) to more efficiently deliver oxygen to the pediatric patient by increasing dead space to recapture a portion of expelled oxygen using

¹ Efficiency gain is based on adult patients. Most conserving devices are not approved for pediatric use.

[figure not shown]
the spatial distribution of the nasal reservoir cannula volume and length of surface seal. This nasal reservoir cannula fits over a standard nasal cannula (also termed prong) (see Fig. 1 below). The system is designed to reduce administered oxygen to deliver an equal or higher fraction of inspired oxygen (FiO₂) per oxygen delivered (L/min) compared with a standard nasal cannula alone. Please refer to the device brochure (Appendix I) for instructional details on the nasal reservoir cannula.

Figure 1. Novel Nasal Reservoir Cannula

[figure not shown]
Mask performance was evaluated using a breathing simulator developed at the Global Good Laboratory (Bellevue, WA). The system consists of a breathing simulator (ASL 5000, IngMar Medical, Pittsburgh, PA) paired with an anatomically correct airway and face constructed by 3D printing computerized tomography scan data (Fig. 2). Carbon dioxide was titrated into the lung to simulate metabolism. The end-tidal carbon dioxide (CO₂), which is equivalent to the maximal concentration of carbon dioxide at the end of an exhaled breath, and FiO₂ were measured. An array of breathing waveforms was tested to bound mask performance.

Figure 2. Pediatric Breathing Simulator

For hospitalized patients with hypoxic respiratory illnesses, the minimal oxygen delivered recommended by the World Health Organization (WHO) is in ranges typically used in low-flow nasal cannulas; in vitro experiments on the breathing simulator indicate that the novel nasal reservoir cannula may be able to provide the same or higher FiO₂ at approximately 2.5-times lower oxygen flow rate (L/min) compared with a standard nasal cannula alone (Global Good, data on file; see Fig. 3). This can result in less oxygen used than conventional delivery systems, which may be valuable for resource limited settings where oxygen supplies are limited.

Figure 3 Oxygen Flow and FiO₂ of Novel Mask (Nasal Reservoir Cannula)

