6.1 Inclusion Criteria

Patients may be included in the study only if they meet **all** of the following criteria:

- [1] Age ≥ 1 and ≤ 6 years.
- [2] Severe pneumonia based on WHO criteria (see Appendix B).
- [3] SpO₂ \geq 85% and < 94% by pulse oximetry on room air.
- [4] Hospital admission based on clinician judgment.
- [5] Written informed consent from parent(s)/guardian(s) of subjects must be obtained before any study procedure is performed.
- [6] Body weight $\geq 8 \text{ kg and } \leq 26 \text{ kg}$

Exclusion Criteria:

Patients meeting any of the following criteria will not be eligible to participate in the study:

- [1] Hypercapnia (pCO₂ > 55 mm Hg or 7.32 kPa) on room air
- [2] Acidosis / lactic acidosis (pH <7.20 and/or lactate >3 mmol/L) on room air
- [3] SpO₂ < 85% or \geq 94% by pulse oximetry on room air
- [4] SICK score > 2.4
- [5] Hemoglobin < 7 g/dL
- [6] Facial abnormalities or trauma precluding use of mask and nasal prongs.
- [7] Requirement of intubation or noninvasive or invasive positive-pressure ventilation.
- [8] Suspected or known pneumothorax.
- [9] Body weight $\leq 8 \text{ kg and} \geq 26 \text{ kg}$
- [10] Hemodynamic instability based on clinician judgment.
- [11] $SpO_2 < 90\%$ by pulse oximetry on oxygen, measured at the end of the enrollment and before initiation of Period 1.

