8.1.5 Withdrawal due to Worsening of Clinical Status

An individual subject will be withdrawn from the study if he or she develops a condition or begins a therapy during the study period that would have excluded entry into the study (e.g., hypercapnia, acidosis, SICK score >2.4, hemodynamic instability, requirement of intubation or positive pressure ventilation, $SpO_2 < 90\%$ on oxygen). Additionally, the onsite pediatrician/Co-Principal Investigator may discontinue investigational device treatment at any time if she feels that further treatment puts the subject at unacceptable risk.

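### The protocol sets no rule for oxygen flow in the mask and cannula hours, so the oxygen-use comparison may mix device effect with staff behaviour

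*Protocol*

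**What the plan says.** Section 4.2.2.1 opens Period 1 with "Patients will be placed on supplemental oxygen consistent with standard of care". Both period lists then carry the item "Record oxygen flow (L/min) every 15 min". The Period 2 list adds no instruction on setting flow. The device brochure (Appendix I) has the user set a flow without giving a value, and leaves the rate to the treating physician.

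The device claim depends on oxygenation being equal. Section 2.2 says reservoir cannulas "usually enable a reduction in the oxygen flow setting of approximately 25 to 50 percent while maintaining the same pulse oxygen saturation". Section 2.3 says of this mask: "The system is designed to reduce administered oxygen to deliver an equal or higher fraction of inspired oxygen". It cites bench work suggesting the same or higher FiO2 at "approximately 2.5-times lower oxygen flow rate (L/min) compared with a standard nasal cannula alone". Appendix I claims up to 50% less flow for the same oxygenation.

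The SpO2 limits on oxygen are safety limits. Exclusion criterion 11 bars a child below 90% on oxygen, "measured at the end of the enrollment and before initiation of Period 1". Section 8.1.5 states: "An individual subject will be withdrawn from the study if he or she develops a condition or begins a therapy during the study period". It means a condition or therapy that meets an exclusion criterion, and it lists SpO2 below 90% on oxygen among its examples. Appendix H repeats this.

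Section 10.4 makes litres used and average flow outcomes. Section 3 says effect sizes from this study are to guide the next trial's power calculation. Section 7.2 describes the trial as open-label.

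**The concern.** Lower flow shows that the mask saves oxygen only if the child is equally well oxygenated in both hours, or if flow is fixed and oxygenation is compared instead. The protocol requires neither.

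Staff who expect the mask to save oxygen may turn flow down further than the device allows. Staff who are cautious, or who see no reason to touch the dial, may leave flow alone although the mask works. Either habit goes with the device rather than with the period, so balancing the order of the two hours does not cancel it.

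At stake is the flow effect size, which could be carried forward too large or too small. An analysis plan could not repair this afterwards, because how flow is set is a matter of bedside conduct.

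**Working it through.** The protocol has no figure of its own to reproduce here: the target of up to 20 patients rests on precedent (Section 10.1). The check has three parts.

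**1. Does any visible text act as a flow rule or oxygenation target?**

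- Section 4.2.2: standard of care, with flow recorded. No value, step or target.
- Appendix I: the physician's judgment. It is a general direction for the mask and says nothing about the cannula-only hour.
- Section 2.2: WHO flow rates for nasal prongs, including 1-4 L/min for older children. These are background, and that range alone is fourfold.
- Section 7.2: care follows WHO recommendations. Appendix B reproduces a WHO rule to give oxygen below 90% saturation, which says when to start and not what to maintain.
- Section 6.1 criterion 11, Section 8.1.5 and Appendix H: below 90% on oxygen means exclusion or withdrawal. This is a floor.

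None of these fixes flow or equalises oxygenation.

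**2. Does the 90% floor hold oxygenation equal in practice?**

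Inclusion criterion 3 admits children at 85% or above "and < 94% by pulse oximetry on room air". A child who enters at 90-93% on room air already meets the floor with little or no oxygen, if the child's condition does not change. For such a child, flow can be cut in one hour and not the other without reaching the floor. The protocol does not say how many children will be in this position.

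**3. How far can the observed saving move?**

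Inputs: cannula flow of 2 L/min (assumed); a 2.5-fold lower flow at equal or higher FiO2 (Section 2.3), which is a true saving of 1 - 1/2.5 = 60%; and a share f of the achievable reduction that staff actually make (assumed).

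Mask litres = 2 x (1 - 0.60 x f) x 60. Cannula litres = 2 x 60 = 120.

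| True device | Flow in the mask hour | Mask litres | Apparent saving |
|---|---|---|---|
| 2.5-fold | fully titrated to equal oxygenation (f = 1) | 0.8 x 60 = 48 | 60% |
| 2.5-fold | half the achievable cut (f = 0.5) | 1.4 x 60 = 84 | 30% |
| 2.5-fold | a quarter of it (f = 0.25) | 1.7 x 60 = 102 | 15% |
| 2.5-fold | left alone (f = 0) | 2.0 x 60 = 120 | 0% |
| inert | halved, SpO2 still at or above 90% | 1.0 x 60 = 60 | 50% |

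The percentages do not depend on the assumed flow. At 1 L/min the fully titrated case is 60 L against 24 L, and at 4 L/min it is 240 L against 96 L; both are 60%. On flow alone, the inert-mask row matches the largest saving the brochure claims.

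**The case against.** The strongest reply is that this is a descriptive feasibility study of up to 20 children, with significance tests only exploratory (Section 10.5.5). Its aims include learning how the intervention is delivered, so watching physicians set flow is part of the purpose. SpO2 and flow are recorded together every 15 min and capillary gases are taken at the end of each hour, so unequal oxygenation would be visible. Much of this stands: no confirmatory test is harmed, and the concurrent readings are useful. But they show that oxygenation differed; they do not replace a rule that makes the flow figures comparable. Section 3 also names effect sizes for the next power calculation as a purpose.

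Four stronger readings are tempting, and the documents do not support them.

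- A reader might infer that the protocol contains no WHO flow guidance. Section 2.2 does reproduce WHO flow ranges, though as background.
- A reader might infer that no flow rule exists anywhere. Figure 4, the appendix material between Appendices C and F, and the cited WHO guideline could not be checked, so the statement is limited to the visible text.
- A reader might infer that a within-child flow difference is the stated analysis. It follows from the crossover design; Sections 10.5.1 and 10.5.5 state only descriptive summaries, by treatment group.
- A reader might infer that the next trial's sample size would be wrong by a known factor. The documents give neither the SD of the flow difference nor the share due to behaviour, and staff behaviour would change the SD as well as the mean.

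**Conclusion.** The point holds in limited form. The visible text leaves flow in both hours to standard of care and physician judgment, with a safety floor but no common oxygenation target. In an open-label crossover, the comparison of litres and flow may therefore mix device effect with staff behaviour. It may do so; the documents do not show that it will.

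In the illustration, the same 2.5-fold device gives anything from 0% to 60%, and an inert mask can give 50%. This rests on the bench figure carrying over to children and on assumed staff behaviour, so it marks what the plan permits and is not an estimate of bias. The consequence is confined to the effect size passed to the next trial.

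**What to change.** In Section 4.2.2, write one procedure that applies to both hours:

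- the same starting flow in each hour;
- titration to one SpO2 band above 90%, chosen by the clinical team, in a stated step at the existing 15-min recording times;
- freedom for the physician to change flow at any time for safety, recorded as an override.

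Alternatively, hold flow fixed in both hours and make SpO2 and capillary PO2 the efficiency comparison. In either case, have Appendix I refer to the procedure, and report the within-child flow difference beside the within-child SpO2 difference.

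This is a cheap improvement: one paragraph, one cross-reference and one table from data already collected. The costs are slightly less bedside discretion, logging of overrides, and an amendment that needs IRB/IEC approval before use (Section 11.2.2). One hour also allows few adjustments: at 15-min intervals, three (at 15, 30 and 45 min) before the hour ends. A band that some children can reach on almost no oxygen would show little flow difference for them, so the clinical team should weigh that when choosing it.

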5 DISCUSSION OF DESIGN

The study is an open-label, prospective, feasibility study of hospitalized pediatric patients with hypoxemia due to severe pneumonia. Patients meeting entry criteria will receive supplemental oxygen consistent with standard of care. Patients will be equally randomized to one of two groups. Group A will receive supplemental oxygen for 1 hr using a novel mask (nasal reservoir cannula) plus standard nasal cannula for 1 hr, followed by a 1 hr period using the standard nasal cannula only. Group B will receive treatment in the reverse order (treatment with standard nasal cannula alone for 1 hr followed by a 1-hr period of novel nasal reservoir cannula plus nasal cannula). Patients with a body weight of 8-13 kg will receive treatment with a small 30 ml mask and patient with a body weight of 14-26 kg will receive treatment with a large 50 ml mask.

The design of this study is consistent with the primary objective of collecting preliminary information to aid in the conduct of a more definitive trial evaluating the safety and efficiency of a novel nasal mask plus nasal cannula (vs. nasal cannula alone) in reducing the total amount of oxygen needed per cylinder for adequate oxygen delivery in pediatric patients with hypoxemic respiratory illness in resource-limited settings. Information on the feasibility of intervention delivery and implementation, trial conduct, availability of patients and recruitment rates, protocol adherence, and effect sizes and outcomes to guide future power calculations and designs will be of value in the design of future trials. The assessments used in this trial are standard assessments for the evaluation of pediatric patients with hypoxemia and severe pneumonia.

6 STUDY POPULATION

The investigators and treating physicians participating in this study have expertise in the diagnosis and management of pediatric patients with hypoxemia and severe pneumonia. The participating institution is the Department of Pediatrics, Makerere University, Kampala, Uganda.

Subjects with hypoxemia and pneumonia will be diagnosed based on history, physical examination, and laboratory indices. Inclusion criteria for this study include patients (age \geq 1 year and \leq 6 years) with severe pneumonia based on WHO criteria that require hospitalization and have hypoxemia (SpO₂ <94%) by pulse oximetry on air.

Participation in this study is voluntary. The nature of the study will be fully explained to each parent(s)/guardian(s) of the patient during the informed consent process. Both verbal and written explanations will be provided to ensure understanding at all literacy levels. The parent(s)/guardian(s) will have the opportunity to ask questions. The participant information sheet and informed consent document (see Appendix E) will be available in English and Luganda. Parents unable to write may document consent with a thumbprint. The informed consent document will then be signed by the patient's parent(s)/guardian(s) and the person performing the consent discussion, and retained by the investigator according to Good Clinical Practice (GCP) guidelines. All documents will be retained at the study site for 3 years beyond study completion according to GCP guidelines. A copy of the signed informed consent (and any signed assent) document will be given to the subject or their parent(s)/guardian(s), or both.

Eligibility for enrollment will be based on the results of screening for the following inclusion and exclusion criteria.

6.1 Inclusion Criteria

Patients may be included in the study only if they meet **all** of the following criteria:

- [1] Age ≥ 1 and ≤ 6 years.
- [2] Severe pneumonia based on WHO criteria (see Appendix B).
- [3] SpO₂ \geq 85% and < 94% by pulse oximetry on room air.
- [4] Hospital admission based on clinician judgment.
- [5] Written informed consent from parent(s)/guardian(s) of subjects must be obtained before any study procedure is performed.
- [6] Body weight $\geq 8 \text{ kg and } \leq 26 \text{ kg}$

Exclusion Criteria:

Patients meeting any of the following criteria will not be eligible to participate in the study:

- [1] Hypercapnia (pCO₂ > 55 mm Hg or 7.32 kPa) on room air
- [2] Acidosis / lactic acidosis (pH <7.20 and/or lactate >3 mmol/L) on room air
- [3] SpO₂ < 85% or \geq 94% by pulse oximetry on room air
- [4] SICK score > 2.4
- [5] Hemoglobin < 7 g/dL
- [6] Facial abnormalities or trauma precluding use of mask and nasal prongs.
- [7] Requirement of intubation or noninvasive or invasive positive-pressure ventilation.
- [8] Suspected or known pneumothorax.
- [9] Body weight $\leq 8 \text{ kg and} \geq 26 \text{ kg}$
- [10] Hemodynamic instability based on clinician judgment.
- [11] $SpO_2 < 90\%$ by pulse oximetry on oxygen, measured at the end of the enrollment and before initiation of Period 1.

6.2 Removal of Subjects from Investigational Device Treatment or Assessment

6.2.1 Early Discontinuation of Investigational Device Treatment

A subject must prematurely discontinue investigational device (nasal reservoir cannula) treatment under any of the following circumstances:

- The subject's parent(s)/guardian(s) wishes investigational device treatment to be discontinued for any reason.
- The investigator wishes the subject to discontinue investigational device treatment, especially, but not limited to the investigator concluding that further treatment puts the subject at unacceptable risk.
- The subject develops a condition or begins a therapy that would have excluded entry into the study (e.g., hypercapnia, acidosis, hemodynamic instability, requirement of intubation or positive pressure ventilation).

A parent(s)/guardian(s) has the right for the subject to discontinue investigational device treatment at any time for any reason without prejudice to current or future medical care by the investigator or other physician at the institution.

